**Precision Orthodontics: A Comparison of Custom vs Traditional
Bracket Treatment Efficiency**

NCT Number: NCT04266769

December 17, 2019

Proposed Investigational Testing

Precision Orthodontics: A Comparison of Custom vs Traditional Bracket Treatment Efficiency

Scope

LightForce Orthodontics' (LFO) investigational testing aims to target multiple investigations sites to examine treatment efficiency metrics using a completely digital and patient-specific bracket treatment system for the correction of malocclusions.

Hypothesis

A fully digital and custom treatment system will provide a more efficient treatment experience compared to standard bracket treatments within the associated orthodontist's experience.

Objective

Compare metrics of treatment efficiency from a traditional "one-size fits all" fixed appliance (FA) system to a fully digital and 3D printed FA system.

Proposed Testing

Significance

Standard orthodontic practices use injection molded stock (not custom; traditional) brackets based on pre-programmed prescriptions to treat all patients with a variety of malocclusions. As each patient's anatomy and malocclusion are unique, this one size fits all approach leads to multiple forms of inefficiencies within a treatment. LightForce Orthodontics offers a digital treatment planning platform and patient-specific 3D printed polycrystalline alumina brackets which combat these inefficiencies and provide a better treatment plan.

The proposed LFO technology receives a digital scan of the patient's anatomy into the treatment planning software where the teeth are digitally moved from their starting position to the desired finishing positions. Brackets are placed in locations which enable Andrews' Straight Wire Appliance (SWA) principles to obtain the final occlusion. Among others, SWA principles dictate that a

treatment is completed when the arch wire no longer has any bends to it. The software program then reconstructs the initial malocclusion with the brackets in the locations which provide the desired outcome. Thus, the orthodontist can begin a treatment knowing exactly where the teeth will end up.

Even with this digital system, a stock bracket would not be able to precisely move the teeth to the desired position. This is due to the aforementioned morphology difference between patients and the inability of a one size fits all bracket to accommodate. The differences between the stock bracket base structure and the tooth surface must be manually filled in with an inexact amount of bonding material yielding inexact positioning which may create unintended movement directions. While the LFO brackets have a similar facial profile to stock brackets, which facilitate standard methods of care, the bracket's base is contoured to match the patient's corresponding tooth morphology. This means that the exact angles of torque, tip, and angulation, which facilitate orthodontic movement, are built into each bracket creating a predictable solution.

In a current standard of care example, the torque of a stock bracket may not be enough to move a tooth into the appropriate finishing angle. In this case, the orthodontist must then bend the arch wire to a certain degree to compound this torque - also known as a third order orthodontic bend. The resulting force is then sufficient to move the tooth to the correct angle. This action may need to be applied to multiple teeth throughout treatment. When a wire bend occurs multiple weeks are added to the desired finishing appointment as the orthodontist must allow the tooth to move and then evaluate the change. Due to the LFO contoured base as well as the SWA principles employed in the LFO System planning process, there should be no need for wire bends during treatment.

Historically, stock brackets must also be placed directly onto the tooth. This can lead to imperfect positioning even by the most experienced orthodontists. This imperfect positioning can either be caused by human-error during placement or because the orthodontist can not anticipate the exact bracket placement that will lead to a perfect finishing occlusion. During treatment the orthodontist must debond the imperfectly placed bracket in favor of a new bracket placed with the same level of insufficient precision. Each replacement extends the finishing appointment date.

This practice of direct bonding could yield inaccurate placement of even perfectly positioned and contoured brackets created using a digital treatment program. To solve this issue, LFO created a 3D printed patient-specific indirect-bonding (IDB) system. Designed directly from the desired bracket placement on the teeth in malocclusion, like a digital mold, the IDB tray precisely matches the tooth anatomy and brackets. Once printed, the corresponding patient's brackets are placed in the IDB tray's bracket wells. The orthodontist can paste the bonding material onto the brackets, while remaining in their specific wells, then place the IDB trays in the patient's mouth and bond the brackets. Once the tray is removed the brackets remain on the teeth in the exact position they were designed for in the treatment planning system.

The presented investigational testing aims to assess treatment efficiency metrics using the LightForce Orthodontic system on a variety of malocclusions across multiple sites compared to the investigator's past experience using traditional bracket systems.

Investigation Design & Participants

This multi-site investigation will evaluate treatment efficiency metrics of different orthodontists using the same LightForce Orthodontic digital treatment planning system and patient-specific brackets. Data collection will include treatment efficiency metrics, participant data such as (but not limited to) gender, age and medical history, and experiential data of standard bracket treatment efficiency metrics. Efficiency metrics may include:

- Treatment length
- Bonding/De-bonding appointment time length
- Length of time to achieve leveling and alignment
- Number of unscheduled appointment
- Number of debonded brackets
- Number of repositioned brackets

All patients that visit the investigation sites are evaluated during initial consultations for their particular medical needs and orthodontic treatment. If a patient is eligible for the investigation, they will be presented with the treatment plan, asked whether they would like to participate, and given a consent form to sign.

There are no specific recruitment materials for this study. However, each orthodontist is provided with a LightForce Orthodontics welcome kit before they enroll their first patient. This includes a typodont, a sample product package (box, brackets in trays and arch form) and patient brochures as pictured below. The patient brochures are not included as study recruitment material.

To run statistical analysis, at least 22 patients must participate at each investigation site to have a power of 90% at a 5% significance level. No patients will be withdrawn from the investigation unless the investigator or patient chooses to discontinue treatment. If there is a lack of compliance with the investigator's treatment plan and/or a developing health condition during treatment, the patient's data may be considered an outlier and not used in statistical analysis.

Inclusion Criteria

- All subjects must be healthy and between the ages of 10 and 65.
- Eruption of all permanent teeth excluding second and third molars
- Sufficient labial tooth surface for bonding
- No more than one tooth missing from a single arch quadrant
- No existing molar tubes or bands

Exclusion Criteria

- Presence of systemic diseases, cleft lip and palate, craniofacial anomalies, syndromes affecting bone or teeth, impacted teeth (excluding 3rd molars), and tumors of the parathyroid gland
- Presence of bridges or implants
- Cases requiring orthognathic surgery
- Significant periodontal disease
- Intake of drugs affecting tooth movement or bone formation (chronic use of Non-Steroidal Anti Inflammatory Drugs, bisphosphonates, levothyroxine, or teriparatide drug class)
- Pregnancy

Clinical Process

Orthodontic treatment process through out this investigation will follow standardized practices. Treatment data will be acquired throughout the following process:

- Facial photos and intra-oral scans will be taken of the patient's teeth
- Treatment will be planned using the LightForce Orthodontics' LF Pro treatment planning system
- LightForce Orthodontics will manufacture and ship the patient-specific brackets to the investigator
- Standard Orthodontic Treatment Progressions
 - Brackets will be bonded to patient's teeth
 - Follow up appointments to change ligatures, move through standard wire progression, and/or replace brackets. The number of appointments can vary based on the patient's treatment plan and progress.
 - Brackets are removed

Conflicts of Interest

The LightForce Orthodontic braces are commercially available in the United States. Every orthodontist in this study will pay LightForce Orthodontics for the LFO System as they would if they were available to purchase in Canada. As such there is no conflict of interest.

However, some investigators are a part of the LightForce Orthodontics' clinical executive board (CEB). If so a [CEB Appendix](#) is attached to their patient's consent form. To also combat any undue influence conflict of interests may have on this study, the investigators chosen are a mix of CEB and non-CEB members. This means any CEB member's data should not influence the overall study

results.

Statistical Analysis

Statistical tests (Student's t-test) will be run to make sure LightForce Orthodontics's Clinical Executive Board (CEB) member treatment group outcomes are not statistically different from non-CEB members within this study. If they are, the data collected from that investigation site will be removed.

We will assume the data will be normally distributed for this study. The primary outcome measures are impacted directly by the patient's age and by the treating orthodontists. Thus the outcome variables will be analyzed through analysis of covariance (ANCOVA) tests controlling for age and orthodontist. Multiple pair wise comparisons may be conducted (t-tests) to determine significant differences between groups. Bonferroni corrections may be conducted to prevent the introduction of Type 1 errors. Multivariate linear regressions may also be used to examine differences in the treatment groups. All statistical tests will be two-sided with a p-value of 0.05 for statistical significance. All statistical analyses will be conducted in a statical software such as SAS software (SAS Institute, Cary, NC).

Risk Assessment

There are no additional risks to participating in this study outside of the standard risks associated with orthodontic treatment. The study does not change the standard method of diagnosis and care for the treatment of malocclusion. The LFO bracket system has been approved by the FDA and is comparable to existing bracket systems. During the approval process, the device underwent standard orthodontic bracket performance tests compared to commercially available devices and biocompatibility tests. These reports can be made available upon request.

Each system is shipped with an instructions for use which contains the following precautions - there are no known adverse reactions or contraindications for this device:

- Due to the hardness of ceramic brackets, bonding brackets in occlusion should be avoided to prevent wearing of enamel surfaces during all phases of treatment.
- LightForce Orthodontic Brackets can withstand all normal torque requirements. However, care should be taken when making torquing activations. Large corrections with full size stainless steel wires may result in bracket failure and should be avoided.
- Instruct not to chew or bite hard substances such as hard candy, ice, or carrots. Careful and thorough patient instruction is key to avoiding appliance or enamel damage.
- LightForce Orthodontic Ceramic Brackets should be avoided in bonding to dental porcelain, restorative or compromised (i.e. large restorations, peg laterals, or pre-existing pathological conditions) enamel surfaces.
- Bonding to porcelain crowns or facings may cause chipping or breakage of the crown or facing during treatment or debonding.

- LightForce Orthodontic Ceramic Brackets are for single patient use only.

Data Monitoring and HIPAA Privacy Protections

All data taken during this study is apart of normal data acquisition for an orthodontic treatment. Each patient will be given a patient alias number. The LFO treatment representative will see identifying information regarding patients but will only record the patient's alias and relevant information for the study. The data collected will not directly link back to the participant's identity which minimizes the risk of a confidentiality breach. Experiential data will be acquired by LFO via communication with the orthodontist. All information is kept on password protected computers and servers. No paper print outs are kept in this study. The signed consent forms are scanned and sent back to LFO through secure emails. The orthodontist can then shred the forms. All personnel involved in this study as well as all members of LightForce Orthodontics are trained on Health Insurance Portability and Accountability Act (HIPAA) privacy rules. The investigators have all been trained on human subjects' research.

The LFO investigators will be responsible for process the data, ensuring the data is de-identified, and confidentiality is maintained. They will also be responsible for internal checks and project oversight. Data will be kept for a minimum of 4 years but up to 7 years after the study completion then destroyed.

Reportable Events

All reportable events will be documented by the treating orthodontist and relayed to the research team at LightForce Orthodontics within 72 hours. LFO will then inform all regulatory bodies deemed necessary within the said time frame.

This mandatory problem reporting includes cases in which the incident:

1. is related to a failure of the device or a deterioration in its effectiveness, or any inadequacy in its labelling or in its directions for use, and
2. has led to the death or a serious deterioration in the state of health of a patient, user or other person, or could do so were it to recur

Reports will be completed within timeframes set (10 or 30 days) within the Investigational Testing Guidance. If a participant feels the need to report any events, contact information is also provided in the consent forms.

Patient Assent/Consent

This investigation provides three types of informed consent forms. For patients under the age of 16 in Canada (18 in Quebec) a [child's assent form](#) must be signed as well as a [parent/guardian's](#)

[consent](#) for child's recruitment. A child may chose to not participate and not sign the assent form even if a parent or guardian has signed the recruitment consent. For patients over the age of 16 (18 in Quebec) a [patient consent form](#) is also provided.

All assent/consent forms are provided in English and French and maintained by LightForce Orthodontics. The investigator will scan the consent/assent form and send it to LFO after consent has been given. The investigator will provide the patient and/or guardian with a copy of their assent/consent form. The signed form will be kept in the [Informed Consent folder](#) at LightForce Orthodontics.

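### The 90% power per site applies only to one uncorrected 5% test; the plan has several primary outcomes, leaves Bonferroni optional, and gives no power at a corrected threshold

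*Combined protocol and SAP*

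**What the plan says.** All references are to the combined protocol and SAP.

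- **Sample size (Investigation Design & Participants):** "at least 22 patients must participate at each investigation site to have a power of 90% at a 5% significance level". The paragraph gives no endpoint, test, effect size, SD or comparator sample size.
- **Outcomes:** the same section lists six bullets, introduced by "Efficiency metrics may include". None is marked as primary. The Statistical Analysis section says "The primary outcome measures are impacted directly by the patient's age and by the treating orthodontists", in the plural, and does not name or rank those measures.
- **Main analysis (Statistical Analysis):** ANCOVA with age and orthodontist as covariates.
- **Further tests:** "Multiple pair wise comparisons may be conducted (t-tests) to determine significant differences between groups".
- **Multiplicity, in the next sentence:** "Bonferroni corrections may be conducted to prevent the introduction of Type 1 errors". The family of tests and the divisor are not given.
- **Threshold:** "All statistical tests will be two-sided with a p-value of 0.05 for statistical significance".

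**The concern.** The sample size is tied to an uncorrected 5% level, yet the plan foresees several primary outcomes and a possible correction. Any Bonferroni correction across outcomes divides 0.05 by at least two, so power per metric falls below the stated figure. The plan does not report the power that would remain.

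Two things are at stake:

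- **Interpretation of a null result.** If the metrics are corrected, a non-significant result at a site would be read against a 90% figure that does not apply to the test performed.
- **A choice left open.** With six metrics the Bonferroni threshold is 0.05/6 = 0.0083. A metric with p between 0.0083 and 0.05 is significant or not depending on a decision that the plan allows to be made after the data are seen.

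**Working it through.** **Inputs from the documents.** n = 22 per site, power 90%, significance level 5%, two-sided tests, six listed metrics.

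**Assumptions.** The effect size and the comparator n are not given. I therefore back-solved the standardized effect d that gives 90% power and held it fixed. Two readings of the 22 are shown: 22 against 22 comparator patients, and 22 against a fixed or paired reference. The number of corrected metrics, m, is also an assumption and is varied.

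**Formula.** Power = P(|T| > t(1 - α/2, df)), where T is noncentral t with noncentrality δ.

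- 22 v 22: df = 42, δ = d × √(22/2).
- One-sample or paired: df = 21, δ = d × √22.

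**Step 1: reproduce 90% at α = 0.05.**

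- 22 v 22: critical value 2.018; 90% power needs δ = 3.318, so d = 3.318/√11 = 1.00.
- One-sample or paired: critical value 2.080; 90% power needs δ = 3.401, so d = 3.401/√22 = 0.725.

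The figures 22, 90% and 5% are thus mutually consistent for some effect size. The documents do not let one check whether that effect was the one intended.

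**Step 2: hold d fixed and set α = 0.05/m.**

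| m | α per test | Critical t (df 42) | Power, 22 v 22 | Critical t (df 21) | Power, one-sample or paired |
|---|---|---|---|---|---|
| 1 | 0.0500 | 2.018 | 90.0% | 2.080 | 90.0% |
| 2 | 0.0250 | 2.325 | 83.6% | 2.414 | 83.0% |
| 3 | 0.0167 | 2.494 | 79.1% | 2.601 | 78.0% |
| 6 | 0.0083 | 2.769 | 70.6% | 2.912 | 68.4% |

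Reading the 22 as a total, 11 v 11, gives 68.2% at m = 6. The normal approximation for 22 v 22 gives 72.7%. The loss therefore depends on m and hardly at all on the reading of the design.

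**Step 3: sample size that would keep 90% per metric at one site.** 27 for m = 2, 29 for m = 3 and 33 for m = 6. These are per group in the two-group reading, and the same numbers result in the one-sample reading.

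**Step 4: pooling.** With two sites pooled (44 v 44, same d, ignoring covariates and variation between sites), δ = 1.00 × √(44/2) = 4.69 with df = 86. Power at 0.05/6 is then about 97%.

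**Step 5: no correction.** Power per metric stays at 90%. Across six independent tests the family-wise error would be 1 - 0.95⁶ = 26.5%.

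**Step 6: Holm in place of Bonferroni.** Holm starts at 0.05/m and relaxes the threshold after each rejection, so it rejects everything Bonferroni rejects and possibly more. In a simulation of the 22 v 22 case with six independent metrics, all with a true effect of d = 1.00, average power per metric was about 84% with Holm and 71% with Bonferroni. That is the favourable case; with fewer real effects the gain is smaller.

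**The case against.** The strongest case against the point has five parts.

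1. **Bonferroni is optional.** The only firm rule is two-sided 0.05, which agrees with the 5% in the sample-size statement. This stands. A reader might infer that the plan sets two contradictory alpha levels, but it does not: 0.05 can also be read as the level for adjusted p-values or for the family. What remains is that the plan never says which reading applies.
2. **The correction may concern only the pairwise t-tests.** The Bonferroni sentence directly follows the one on those tests, and this is a natural reading. The documents do not show that the correction covers the test behind the 90%. Neither do they exclude it, since the sample-size statement names no test. The scope must be stated.
3. **Six is not the plan's number.** The list is non-binding and the primary measures are not counted. This stands, so the six-metric figure is one end of a conditional range.
4. **Pooling restores power.** An ANCOVA controlling for orthodontist points to a pooled analysis, and two pooled sites would exceed 90% even at 0.05/6. This stands for the trial as a whole. The sample-size claim is made for each site, however, and the figures above check that claim.
5. **Holm is a matter of preference.** In part. The essential step is to fix a rule in advance over named metrics. Given that some correction is contemplated, Holm controls the same error rate as Bonferroni and never has less power.

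**Conclusion.** The point holds in conditional form. The stated 90% applies to one uncorrected two-sided 5% test at one site. If Bonferroni were applied across the outcome metrics, power per metric at one site would be about 83-84% for two metrics, 78-79% for three and 68-71% for six. At six, the chance of missing the assumed effect in a given metric rises from 10% to about 30%.

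These figures rest on t-tests, a back-solved effect (d about 1.00 or 0.725, depending on the reading) and single-site analysis.

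A reader might go further and infer that the design has 68-71% power instead of 90%. The documents do not support that: the correction is permitted but not mandated, its scope and divisor are unstated, and pooling would raise power. Nor is 22 shown to be miscalculated; without an effect size, SD and comparator n, it can be neither confirmed nor refuted.

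**What to change.** Keep n and change two paragraphs.

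1. **Statistical Analysis.** Name the primary metrics. Replace the optional Bonferroni sentence with a pre-specified Holm procedure over those metrics at family-wise two-sided 0.05. Make the 0.05 sentence refer to Holm-adjusted p-values for the primary metrics.
2. **Sample-size paragraph.** State that 90% is the power of one uncorrected two-sided 5% test at one site. Add the assumed effect size and the power at the corrected threshold for the number of primary metrics chosen. Under the back-solved effect, power at 0.05/m is about 83-84% for two metrics and 68-71% for six. Because 0.05/m is Holm's strictest step, these are lower bounds for Holm.

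**Cost.** Wording only, and no additional patients. The stated power becomes less favourable, and some metrics face a stricter threshold than 0.05. In return, the choice of threshold can no longer be made after the data are seen.

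### Enrolled patients may be dropped as outliers for events after treatment starts, with no operational rule, no stated counterpart for the traditional figures and no all-treated analysis

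*Combined protocol and SAP*

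**What the plan says.** The rule follows the sample-size sentence under Investigation Design & Participants. Withdrawal comes first: "No patients will be withdrawn from the investigation unless the investigator or patient chooses to discontinue treatment". The next sentence names two triggers: "If there is a lack of compliance with the investigator's treatment plan and/or a developing health condition during treatment". The stated consequence of either one is that "the patient's data may be considered an outlier and not used in statistical analysis". Neither trigger has a definition or threshold. The person who decides is not named, and nothing says that the decision comes before outcomes are seen.

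The Clinical Process section has every enrolled patient planned on the sponsor's software and treated with its brackets. The last paragraph of the Significance section says that results are "compared to the investigator's past experience using traditional bracket systems". Under Data Monitoring and HIPAA Privacy Protections, the source of those figures is given: "Experiential data will be acquired by LFO via communication with the orthodontist". No exclusion is stated for them.

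The Statistical Analysis section says: "Thus the outcome variables will be analyzed through analysis of covariance (ANCOVA) tests controlling for age and orthodontist". It also says: "All statistical tests will be two-sided with a p-value of 0.05 for statistical significance". It defines no analysis population and names no all-treated or sensitivity analysis. Its only other exclusion is removal of site data when outcomes differ between members and non-members of the sponsor's clinical executive board, which does not bear on this point.

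**The concern.** An outlier is normally an extreme value. Here the label goes to a patient because of something that happened after bonding, whether or not the outcome is extreme. Non-compliant or ill patients may plausibly have longer treatment, more debonded brackets and more unscheduled visits, all of which are listed efficiency metrics. Leaving them out then improves the LFO average. If the traditional figures still contain such patients, part of the apparent advantage comes from selection and not from the device.

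The trigger can also overlap with the outcome. Compliance is undefined, and the precautions under Risk Assessment tell patients to avoid hard foods that could damage the appliance. A patient with a broken bracket could therefore be called non-compliant and removed together with the event being counted. The plan does not say that this will happen, but nothing in it prevents it. Other metrics, such as time at the bonding appointment, may not be affected.

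**Working it through.** **The plan's own figure.** At least 22 patients per site, for 90% power at 5%. It cannot be reproduced, because no effect size, SD or test is given. Solving backwards with the t distribution (two-sided 5%, 90% power), 22 patients correspond to 0.725 SD in a one-sample comparison, or about 1.00 SD with 22 per group. These two effects are used for power in step 4.

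**Inputs not in the documents.** The share of non-compliant or ill patients, how far they differ, the SD, the number of sites and the make-up of the traditional figures are all missing. The values below are assumptions: share p = 10% or 20%; difference δ in SD units of the other patients; all such LFO patients excluded; no true device effect.

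**Step 1: size of the shift.** With fraction f excluded, mean(all) = (1 − f) × mean(kept) + f × mean(excluded). Hence mean(all) − mean(kept) = f × [mean(excluded) − mean(kept)]. At δ = 1 this is 0.10 × 1 = 0.10 SD or 0.20 × 1 = 0.20 SD. The shift does not depend on the number of patients, so adding sites does not dilute it.

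**Step 2: false LFO-better rate at one site under the current rule.** The nominal rate is 2.5%, half of the two-sided 5%. The traditional figures are assumed to include all such cases. Simulated, 200,000 trials, rounded; paired entries are for 10% / 20% excluded.

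| δ (excluded minus kept) | Shift | 22 enrolled v fixed benchmark | 22 enrolled v 22 traditional |
|---|---|---|---|
| 1 SD | 0.10 / 0.20 toward LFO | 6% / 12% | 5% / 8% |
| 0.5 SD | 0.05 / 0.10 toward LFO | 4% / 6% | 4% / 5% |
| 0 | 0 | 2.5% / 2.5% | 2.5% / 2.5% |
| −0.5 SD | 0.05 / 0.10 against LFO | 1.5% / 0.9% | 1.7% / 1.2% |

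**Step 3: what the traditional figures contain.** Let them omit a fraction g of such cases. Their mean is then δp(1 − g)/(1 − pg), measured from the mean of the kept patients.

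- Current rule: shift toward LFO = δp(1 − g)/(1 − pg).
- All treated patients kept: the LFO mean is δp, so shift against LFO = δp − δp(1 − g)/(1 − pg) = δpg(1 − p)/(1 − pg).

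At δ = 1, for p = 10% / 20%:

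| g | Current rule, toward LFO | All treated kept, against LFO |
|---|---|---|
| 0 | 0.10 / 0.20 SD | 0 |
| 0.5 | 0.05/0.95 = 0.053 / 0.10/0.90 = 0.111 SD | 0.045/0.95 = 0.047 / 0.08/0.90 = 0.089 SD |
| 1 | 0 | 0.10 / 0.20 SD |

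At g = 1, the all-treated analysis gives a simulated false LFO-worse rate of about 5% / 9% (22 v 22) or 6% / 13% (fixed benchmark). It returns to about 2.5% only at g = 0.

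**Step 4: power, keeping everyone v the current rule.** Keeping everyone raises the SD to √(1 + p(1 − p)δ²), which at δ = 1 is √1.09 = 1.044 or √1.16 = 1.077. The current rule leaves about 20 or 18 of 22 (22 × 0.9 = 19.8; 22 × 0.8 = 17.6). Powers are from the noncentral t distribution. Those for the current rule take an SD of 1 and ignore the shift itself.

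| Comparison | All kept | Current rule |
|---|---|---|
| One-sample | 87.4% / 85.3% | 86.8% / 82.6% |
| Two-sample | 87.4% / 85.3% | 88.5% / 86.6% |

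**The case against.** Four points on the other side deserve weight.

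- The sentence follows the one on discontinuation and may be meant only for disrupted treatment. That is possible. But discontinuation has its own sentence, and the wording does not stop a patient who completes treatment from being dropped.
- A compliant-and-healthy analysis answers a fair question, since entry already requires that "All subjects must be healthy and between the ages of 10 and 65". This stands. The gap is that no all-treated result sits beside it.
- The direction is not established. This also stands: the shift is zero or reversed under some assumptions. The tabulated rates also take every such LFO patient as excluded, although the plan says only that they may be.
- The experiential comparator is a larger weakness. It is, and no change to the exclusion rule cures it, but the exclusion rule can be repaired separately.

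Two stronger readings are tempting. A reader might infer that the exclusion is applied to LFO patients only. The documents support less: no counterpart is stated for the traditional figures, and whether those figures are screened in the same way is unknown. A reader might also infer that keeping all treated patients restores the nominal error rate. That holds only if the traditional figures include all such cases. If they omit half, keeping everyone mostly exchanges one shift for another of similar size in the opposite direction.

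**Conclusion.** The point holds as a gap in the definition of the analysis set. A discretionary exclusion based on events after treatment starts, with no all-treated companion and no stated counterpart for the comparator, can tilt the comparison. The reader cannot tell from the plan whether it does. The true size is unknown. The rise from 2.5% to 6% / 12% or 5% / 8% illustrates 10% / 20% excluded at a 1 SD difference, with every such case present in the traditional figures. It is not an estimate for this trial. The documents do not support a claim that the result will favour LFO, or that an all-treated analysis is unbiased in itself. The matter should be fixed. Confidence is medium, because the effect depends on figures that the documents do not give.

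**What to change.** Replace the outlier sentence with:

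> The primary analysis includes all patients in whom LFO brackets are bonded, regardless of compliance or health conditions that develop during treatment. An analysis leaving out such patients is a sensitivity analysis, with criteria fixed before outcomes are reviewed, reported beside the primary result with the number and reasons for exclusion by site.

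State one exception. Treatment length exists only for patients who complete, so report it for all completers regardless of compliance or health, with the number who discontinued at each site beside it.

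Ask each orthodontist whether the traditional figures include non-compliant and ill patients, and fix the reading in advance:

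- If they are included, the all-treated comparison is the like-for-like one.
- If they are omitted, the all-treated comparison is tilted against LFO when such patients run longer, and the matched sensitivity analysis is the like-for-like one.
- If this is unknown, state that either analysis may be one-sided, and draw no conclusion that depends on which is used.

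The cost is one sentence replaced, a short reporting rule, one question per orthodontist and a little more analysis work, with no extra patients or visits. The LFO mean may look less favourable. Against the current rule at the same assumed rates, one-site power is about unchanged or higher in a one-sample comparison (by 0.6 or 2.7 points) and about 1 point lower in a two-sample one. The change does not make up for the lack of case-level comparator data.
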